Does a Pre-transplant Health Coaching Intervention for Informal Caregivers of Adult Heart or Lung Transplant Candidates Improve Caregiver-Reported Outcomes?

NCT04245228

February 20, 2020

IRB Minimal Risk Protocol Template

Note: If this study establishes a human specimen repository (biobank) for research purposes, do not use this template. Use the Mayo Clinic Human Specimen Repository Protocol Template found on the IRB home page under Forms and Procedures at http://intranet.mayo.edu/charlie/irb/

First-time Use: Use this template to describe your study for a new IRB submission.

- 1. Complete the questions that apply to your study.
- 2. Save an electronic copy of this protocol for future revisions.
- 3. When completing your IRBe application, you will be asked to upload this document to the protocol section.

Modification: To modify this document after your study has been approved:

- 1. Open your study in IRBe. Click on the study 'Documents' tab and select the most recent version of the protocol. Save it to your files.
- 2. Open the saved document and activate "Track Changes".
- 3. Revise the protocol template to reflect the modification points, save the template to your files
- 4. Create an IRBe Modification for the study and upload the revised protocol template.

General Study Information

Principal Investigator: [name]

Study Title: Wellness Coaching for Caregivers of Thoracic Transplant Candidates

Protocol version number and date: Version 2 – February 20, 2020

Research Question and Aims

Hypotheses: Caregivers will have traits and behaviors pre-transplant that will predict caregiver readiness, quality of life, and transplant recipient outcomes. Specifically, thoracic pre-transplant caregivers report stress, symptoms of anxiety or depression, and perceive high caregiver burden. These factors may be amenable to pre-transplant intervention to improve overall patient and caregiver outcomes.

Aims, purpose, or objectives: We will conduct a pilot trial to test whether caregivers of heart and lung transplant candidates who receive wellness coaching will experience improvement in caregiver-related distress. We will also explore the relationship between caregiving and factors such as uncertainty, resilience, stress level, and affect.

Background (*Include relevant experience, gaps in current knowledge, preliminary data, etc.*): Heart and lung transplant recipients experience a range of psychosocial and medical issues for the duration of the transplant experience, including the initiation of the transplant evaluation, pre-transplant waiting period, perioperative recovery, and long-term adjustment post-transplant. Throughout the process, family caregivers play a major role in maintaining their loved ones' physical and mental health but also undergo exposure to the stressors of

transplantation. Current evidence describes high stress, caregiver burden, and increased mood disorders in the pre-transplant caregiver journey. Currently, limited resources and interventions have been trialed in thoracic transplant caregivers to improve this distress.

Study Design and Methods

Methods: Describe in lay terms, completely detailing the research activities that will be conducted by Mayo Clinic staff under this protocol.

This is a pilot study examining the effects of a health coaching intervention on the stress and burden of caregivers of patients awaiting heart or lung transplant.

Identifying Caregivers for Participation

Potentially eligible caregivers for Mayo Clinic waitlisted adult heart, heart-lung, or lung transplant candidates (including names, address, and phone numbers of caregivers) will be acquired through the electronic medical record of the Mayo Clinic adult heart and lung transplant waitlisted patients. For waitlisted heart and lung transplant candidates without a caregiver specified in the medical record (including patients deferred, active, or with a waiting list status of "temporarily inactive"), they will be sent via mail, PTRAX or Redcap an IRB-approved contact letter including information about this study as well as a caregiver nomination form and a HIPAA form. Patients will have the opportunity to nominate up to 3 caregivers for participation in this study, or they may decline to nominate any caregivers. Non-responders will be contacted by phone to ask for caregiver nominations.

In addition, self-referral or word-of-mouth caregiver referrals would be considered if they otherwise met eligibility criteria. Due to current practices of multi-site listing in the Mayo Clinic Transplant Enterprise, caregivers for patients on the heart and lung transplant lists at Mayo Florida or Mayo Arizona may also be considered for inclusion. Additionally, caregivers for heart or lung transplant patients at the Mayo Clinic who subsequently transfer their listing to a different (non-Mayo) transplant center would continue to be eligible for the study unless they withdrew consent. Likewise, caregivers for heart or lung transplant candidates who receive their organ transplant during the course of the health coaching intervention would remain eligible to complete the study unless they withdrew consent.

Approaching Caregivers for Participation

Nominated caregivers or caregivers identified through the electronic medical record may be contacted by phone, mail, or in person to determine interest in this study. Caregivers not interested will have a mechanism to send a refusal. Non-responders will be sent a second interest letter. If the study team does not receive any correspondence from the caregiver, recruitment calls will be attempted 3 times. If the study team is unable to reach the caregiver for a call after 3 attempts, the participant will be declared a non-responder. Caregivers may be contacted while the patient is deferred or active on the transplant waitlist. If a waitlisted patient is transplanted, then the caregiver's eligibility for recruitment will end once the transplanted patient is discharged

from the hospital. In such cases, a caregiver's enrollment, baseline questionnaires, and randomization need to be complete prior to a patient's post-transplant discharge in order for the caregiver to proceed with the study.

Caregivers who agree to participate in this study will be randomized to either receive a wellness coaching intervention in which they will be assigned a wellness coach trained in motivational interviewing who will call the patient weekly for 12 sessions for an approximately 30-minute intervention or usual care (routine caregiver transplant education). Randomization will be stratified to type of transplant the patient they are caring for is waiting to receive (e.g. heart or lung). Participants who miss a call will be allowed a make-up call with the goal of finishing 12 calls over a 16-week period. The wellness coaching calls will be recorded and externally monitored by an independent expert to assure treatment fidelity, and all recordings will remain private. After completion of the intervention, all participants will be asked to complete the questionnaires a second time in addition to a qualitative/satisfaction survey by phone mail or by Redcap. Demographic data will be collected at the time of the initial questionnaires and verified with the follow-up questionnaires. If a participant leaves large sections or multiple pages of the questionnaires unanswered, they will be sent an IRB-approved letter asking that they complete the unanswered questions or indicate that the questions were purposely left unanswered. Psychometric surveys will be stored in a locked cabinet. Data will be entered into a secure password-protected REDCap database. Questionnaire and qualitative data will be kept in a password-protected REDCap database on our secure network. Audio files from health coaching sessions will also be stored in a password-protected folder on our secure network.

Study Measures:

- 1. Demographic information: Participations will be asked to self-report their sex, race, ethnicity, marital status, education level, type of transplant the patient they are caring for is waiting to receive, waiting time duration, and the relationship to transplant recipient to whom they are a caregiver.
- 2. Questionnaires:

PROMIS Global Health – Mental 2a PROMIS Global Health – Physical 2a PROMIS Satisfaction with Social Roles and Activities – Short Form 4a PROMIS Social Isolation – Short Form 4a Chew (2004) Health Literacy Screening Questions RISC – 10 PANAS Zarit Burden Interview Perceived Stress Scale Patient Health Questionnaire-2 (PHQ-2) Generalized Anxiety Disorder -2 (GAD-2)

Subject Information

Target accrual is the proposed total number of subjects to be included in this study at Mayo Clinic. A "Subject" may include medical records, images, or specimens generated at Mayo Clinic and/or received from external sources.

Target accrual: 60 patients and 60 caregivers

Subject population (children, adults, groups): Caregivers of adult patients on the heart and lung transplant waiting lists

Inclusion Criteria: Aged 18 or older who are the primary caregivers of patients listed (active, deferred, or temporarily inactive) for lung, heart/lung, or heart transplantation at Mayo Clinic in Rochester and Jacksonville, FL

Exclusion Criteria: Individuals younger than 18 will be excluded. Those who are non-English speaking, non-verbal, or extremely hard of hearing will also be excluded.

Review of medical records, images, specimens

Check all that apply (data includes medical records, images, specimens).

Only data that exists before the IRB submission date will be collected.

Date Range for Specimens and/or Review of Medical Records: Examples: 01/01/1999 through 12/31/2015, or all records through *mm/dd/yyyyy*.

Note: The Date Range must include the period for collection of baseline data, as well as follow-up data, if applicable.

X The study involves data that exist at the time of IRB submission **and** data that will be generated after IRB submission. Include this activity in the Methods section. Examples

• The study plans to ask subjects to complete a questionnaire.

The study will use data that have been collected under another IRB protocol. Include in the Methods section and enter the IRB number from which the research material will be obtained. *When appropriate, note when subjects have provided consent for future use of their data and/or specimens as described in this protocol.*

Enter one IRB number per line, add more lines as needed

🗌 Data	Specimens	Data & Specimens	
🗌 Data	Specimens	Data & Specimens	

Data Specimens Data & Specimens

Data Analysis

Power analyses may not be appropriate if this is a feasibility or pilot study, but end-point analysis plans are always appropriate even if only exploratory. Provide all information requested below, or provide justification if not including all of the information.

Power Statement: Not required for a pilot study.

Data Analysis Plan: Descriptive statistics and change in secondary endpoints.

Endpoints

Primary: Acceptability and feasibility of wellness coaching for caregivers of thoracic transplant candidates. This will be obtained by looking at completion rate of intervention and qualitative surveys after the intervention is completed.

Secondary: Preliminary efficacy data for power calculation for larger R01 application and multisite study. We will look at change in reported outcomes of stress, caregiver burden, resilience, quality of life, affect, and mastery.

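### The only aim about the intervention is a test of efficacy, but the primary endpoint is feasibility and the analysis plan compares no arms

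*Combined protocol and SAP*

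**What the plan says.** Research Question and Aims states the trial's purpose as "We will conduct a pilot trial to test whether caregivers of heart and lung transplant candidates who receive wellness coaching will experience improvement"; the outcome meant is distress linked to the caregiving role. One further aim follows: "We will also explore the relationship between caregiving and factors such as uncertainty, resilience, stress level, and affect". That aim is exploratory and does not concern the intervention. The opening of the Methods repeats an effects purpose: "This is a pilot study examining the effects of a health coaching intervention on the stress and burden of caregivers". None of these sentences mentions feasibility or acceptability.

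The Endpoints section has a different order of priority. It gives "Primary: Acceptability and feasibility of wellness coaching for caregivers of thoracic transplant candidates", and on measurement it says "This will be obtained by looking at completion rate of intervention and qualitative surveys after the intervention is completed". Caregiver outcomes come second: "Secondary: Preliminary efficacy data for power calculation for larger R01 application and multisite study". Six outcome domains are then listed, stress and caregiver burden among them. None is called distress, and none is singled out.

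The Data Analysis section says "Power Statement: Not required for a pilot study". Its analysis plan is a single line that covers descriptive statistics and change in the secondary endpoints. The Methods randomize caregivers to coaching or usual care, stratified by transplant type, and ask all participants to repeat the questionnaires after the intervention. No between-arm estimate, test, model or confidence interval is specified.

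**The concern.** A trial's aim, primary endpoint and analysis should answer the same question. Here the aim promises a test of whether coaching works, the primary endpoint asks whether coaching can be delivered and is acceptable, and the analysis describes scores and their change without saying how the randomized arms will be compared.

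Followed as written, the plan would answer its stated aim only with descriptive change. Change within the coached arm cannot be separated from what would have happened under usual care, and that is the comparison the randomization was set up to provide. A reader who holds the trial to its stated aim could also take a non-significant difference as evidence that coaching does not help, or a chance significant one as evidence that it does. Meanwhile feasibility, which the Endpoints section treats as the main question, is nowhere stated as an aim.

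**Working it through.** **Side by side**

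| Section | What it makes the main question |
|---|---|
| Research Question and Aims | Test whether coaching improves distress |
| Methods, opening sentence | Effects on stress and burden |
| Endpoints, primary | Acceptability and feasibility |
| Endpoints, secondary | Preliminary efficacy data to power a later study |
| Data Analysis | Description and change; no between-arm comparison |

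The first two rows agree with each other, and so do the last three. The two groups do not agree.

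**How much a test could show.** The documents state no power, significance level, allocation ratio, effect size or dropout, so there is no figure of the plan's own to reproduce. The one input from the documents is the target of 60 caregivers (Subject Information). The assumptions are 1:1 allocation, so 60 / 2 = 30 per arm; a two-sided 5% level; an effect d in SD units; and losses of 0% or 20%, the latter leaving 30 × 0.8 = 24 per arm.

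Normal approximation: power = Φ(d × √(n/2) / s − 1.96), where s = 1 unadjusted and s = √(1 − r²) with adjustment for a baseline score that correlates r with follow-up.

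- n = 30, d = 0.5, unadjusted: 0.5 × √15 = 1.936; Φ(1.936 − 1.96) = 49%. The two-sample t-test gives 48%.
- n = 30, d = 0.5, r = 0.5: s = 0.866; 1.936 / 0.866 = 2.236; Φ(0.276) = 61%.
- n = 30, d = 0.5, r = 0.7: s = 0.714; 1.936 / 0.714 = 2.711; Φ(0.751) = 77%.
- n = 24, d = 0.5, unadjusted: 0.5 × √12 = 1.732; Φ(1.732 − 1.96) = 41%. The t-test gives 40%.
- n = 24, d = 0.5, adjusted: r = 0.5 gives Φ(1.732 / 0.866 − 1.96) = 52%; r = 0.7 gives Φ(1.732 / 0.714 − 1.96) = 68%.

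For other effects at 30 per arm, unadjusted t-test power is 21% at d = 0.3 and 86% at d = 0.8, and 80% is reached at d = 0.74. At 24 per arm, 80% needs d = 0.83.

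**What an estimate would give.** The half-width of the 95% interval for the between-arm difference is 1.96 × s × √(2/n). Unadjusted, this is 0.51 SD at 30 per arm and 0.57 SD at 24. Adjusted at 30 per arm, it is 0.506 × 0.866 = 0.44 SD for r = 0.5 and 0.506 × 0.714 = 0.36 SD for r = 0.7. Such an interval is wide, but it is the information a later study needs.

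**The case against.** The strongest reply is that the protocol calls itself a pilot in the aim sentence and again in the Methods, and that the Endpoints section labels the efficacy data preliminary. On that view the fault is one over-assertive verb and a missing feasibility aim. This is largely fair, and it is why the point is one of alignment and not of a failed design. It does not remove the mismatch. The form's own guidance under Data Analysis lets a pilot do without a power analysis but still expects an analysis plan for the endpoints.

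Several stronger readings are tempting, and the documents do not support them.

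- *The missing power statement is a defect.* It is not. The waiver is reasoned and usual for a pilot, and nothing here calls for a larger trial.
- *The aim speaks of caregivers who receive coaching, so an as-treated comparison is intended.* The Methods use the same verb for allocation, and nothing else points to an as-treated analysis.
- *The title proves an efficacy trial.* The cover heading does ask "Does a Pre-transplant Health Coaching Intervention for Informal Caregivers of Adult Heart or Lung Transplant Candidates Improve Caregiver-Reported Outcomes", but the Study Title given under General Study Information is neutral.
- *The trial could show nothing about efficacy.* A 0.8 SD effect would be detected with 86% power at 30 per arm if a test were done, and baseline adjustment helps with smaller effects.

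It can also be said that the power figures describe an analysis nobody has planned and rest on assumptions. That stands. They serve only to show why the word test is unwise here.

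**Conclusion.** The only aim about the intervention does not match the primary endpoint or the analysis plan, and the plan specifies no use of the randomized comparison. This is clear from the text and needs no assumption.

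The size of the consequence does rest on assumptions (1:1, two-sided 5%, 0.5 SD, loss of 0% or 20%). With 30 per arm, a real 0.5 SD effect would be missed about 52% of the time unadjusted, and about 23% to 39% of the time with baseline adjustment at correlations of 0.7 to 0.5. With 24 per arm the unadjusted figure is about 60%. None of the 0.5 SD cases examined reaches 80% power. That supports reporting distress outcomes as estimates with intervals. It does not support a claim that the trial is too small for its purpose as a pilot.

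**What to change.** Two changes, which can go in one modification.

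1. In Research Question and Aims, and in the opening sentence of the Methods, make feasibility and acceptability of coaching the first aim. Make the secondary aim to estimate the effect of coaching, compared with usual care, on caregiver stress and burden. Changing only one of the two places would leave the mismatch in the other.
2. In the Data Analysis Plan, add the baseline-adjusted between-arm difference in follow-up score, by randomized group, with a 95% confidence interval, for the Perceived Stress Scale and the Zarit Burden Interview. Both are already among the Study Measures. Describe these results as preliminary and not as a confirmatory test of efficacy.

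Naming two instruments also settles what distress means for the secondary aim. The cost is a less ambitious stated aim and a little more analysis work. Sample size, questionnaires and procedures do not change. Rewording the aim will not supply a completion definition or success threshold for feasibility, which the Endpoints section does not give.

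### The second questionnaires are due after the intervention is completed, a date that depends on adherence in the coaching arm and is undefined for usual care and for caregivers who stop coaching

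*Combined protocol and SAP*

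**What the plan says.** All references are to the combined protocol and SAP.

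- **Follow-up trigger** (Study Design and Methods, Approaching Caregivers for Participation): "After completion of the intervention, all participants will be asked to complete the questionnaires a second time". A satisfaction survey goes out at the same time. The document gives no other rule for follow-up timing.
- **Coaching schedule** (same section): the coach will "call the patient weekly for 12 sessions" (from context, the caregiver is the one called). Missed calls may be made up, "with the goal of finishing 12 calls over a 16-week period".
- **Comparator** (same section): usual care, described only as the standard transplant education for caregivers. It has no sessions, duration or end date.
- **Transplant around the study period**: if the patient is transplanted before the caregiver is enrolled, the caregiver's enrolment, "baseline questionnaires, and randomization need to be complete prior to" the patient's discharge from hospital. Caregivers whose patients "receive their organ transplant during the course of the health coaching intervention would remain eligible to complete the study", unless consent is withdrawn (Identifying Caregivers for Participation).
- **Size and analysis**: "Target accrual: 60 patients and 60 caregivers" (Subject Information); "Descriptive statistics and change in secondary endpoints" (Data Analysis).
- **Endpoints**: the primary endpoint, acceptability and feasibility, rests on "completion rate of intervention and qualitative surveys after the intervention is completed". The secondary endpoints are changes in caregiver-reported outcomes, wanted as early efficacy data for sizing a later, larger study.

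**The concern.** A change score needs a defined second time point. Here that point is an event, and the event behaves differently in the two arms. In the coaching arm it moves with missed and made-up calls, so a post-randomisation behaviour sets the outcome date. In usual care there is no intervention to complete, and caregivers who stop coaching never complete it. Both groups are nevertheless among those to be assessed.

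Elapsed time may matter in this population. A caregiver's baseline can fall as late as the patient's transplant admission, and a patient can be transplanted while coaching is under way, so the caregiver's situation may change within weeks. If one arm is measured later than the other, part of an observed difference in change could reflect where each family stands in the transplant course. Randomisation balances the arms at baseline; it does not equalise assessment times chosen afterwards.

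What is at stake is the secondary efficacy data that are meant to feed a later power calculation.

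**Working it through.** The plan gives no power, effect size or timing figure to reproduce. The check is arithmetic on the call schedule, followed by a scale for judging a timing gap.

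**1. Earliest and latest follow-up for coaching completers**

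- Twelve weekly calls have 11 intervals. With the first call in week 1, the last falls in week 12, which is 11 weeks after the first.
- Under the 16-week goal, the last call falls in week 16 by week number, or 16 elapsed weeks after the first call on the longer reading.
- Spread: 16 − 12 = 4 weeks by week number, or 16 − 11 = 5 weeks on the longer reading.
- Neither figure is a ceiling, because 16 weeks is a goal and no cut-off is stated.

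**2. The other groups**

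| Group | Date of completing the intervention |
|---|---|
| Coaching, no missed calls | about week 12 from first call |
| Coaching, calls made up within the goal | up to about week 16 |
| Coaching, goal missed | later, no limit stated |
| Stopped coaching | not defined |
| Usual care | not defined; no first call to count from |

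The interval from baseline or randomisation to the first call is not stated either.

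**3. Illustrative gap between arms**

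Assume that all coached caregivers finish within the goal, spread evenly, and that usual care is measured at a single week inside the same range.

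- By week number: coaching mean (12 + 16)/2 = 14, so the mean gap is 0 to 2 weeks.
- On the longer reading: coaching mean (11 + 16)/2 = 13.5, so the mean gap is 0 to 2.5 weeks.
- If usual care were instead timed from randomisation, the lag to the first call could add to the gap. With an assumed lag of 1 to 4 weeks, the 2-week gap becomes 3 to 6 weeks.

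**4. Scale: what drift would matter?**

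Timing bias = drift per week × gap in weeks. The documents give no drift rate, so only a break-even against one standard error can be shown. Assumptions: 60 caregivers split 30 and 30, all returning follow-up; equal SDs at both times; baseline-to-follow-up correlation r between 0.3 and 0.7.

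- SE of the difference in mean change = SD × √(2/30) × √(2(1 − r)), with √(2/30) = 0.258.
- r = 0.3: 0.258 × √1.4 = 0.306 SD. r = 0.5: 0.258 SD. r = 0.7: 0.258 × √0.6 = 0.200 SD.

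| Gap (weeks) | Drift at which bias equals one SE (SD per week) |
|---|---|
| 2 | 0.200/2 to 0.306/2 = 0.10 to 0.15 |
| 2.5 | 0.200/2.5 to 0.306/2.5 = 0.08 to 0.12 |
| 4 | 0.200/4 to 0.306/4 = 0.05 to 0.08 |
| 5 | 0.200/5 to 0.306/5 = 0.04 to 0.06 |

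These figures are a yardstick only. They do not estimate the bias.

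**The case against.** The strongest reply is that the sentence covers all participants, so follow-up of both arms is clearly intended, and that completion can sensibly be read as the end of the intervention period. On that reading 16 weeks might serve as an implied common date. The first part stands: the gap concerns when caregivers are assessed, not whether they are. The second does not close it, because the 16 weeks are attached to finishing calls and are not linked to the questionnaires, to usual care or to a start date.

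It can also be said that no between-arm comparison of change is written down. That is correct. The comparison is an inference from the randomised design and the stated efficacy purpose, and the concern depends on that inference.

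A third reply is that naming a usual-care equivalent, or simply recording dates, would change less. Recording dates is worth doing, but outcome timing would still follow adherence in one arm only.

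Four stronger readings are tempting and are not supported:

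- A reader might infer that assessment times will differ and that the comparison is biased. The text permits this but does not show it.
- A reader might infer that usual-care caregivers or those who stop coaching go unassessed. The Methods wording says otherwise.
- A reader might infer from the Endpoints section that the satisfaction survey is for completers only. The Methods section sends it to all participants.
- In the opposite direction, a reader might conclude that any timing bias must be smaller than sampling error. With no drift rate in the documents, that cannot be claimed either.

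**Conclusion.** The concern holds, as a minor point and a cheap improvement. The only follow-up rule ties the outcome date to adherence in one arm and gives no date for usual care or for caregivers who stop coaching. Among coached caregivers who finish within the goal, follow-up can vary by about 4 weeks by week number (5 on the longer reading), and by more if the goal is missed.

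Whether the arms would differ in practice, in which direction, and by how much the change scores would shift cannot be determined from the documents. The break-even figures rest on assumed 1:1 allocation, complete follow-up, equal SDs and an assumed correlation; the gaps rest on assumed finishing patterns.

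The reach is limited. The outcomes concerned are secondary and descriptive, and the coaching completion rate does not depend on when the questionnaires are sent.

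**What to change.** In the Methods section, replace the completion trigger with one assessment time counted from randomisation, with the same window in both arms. Apply it whatever the number of calls completed, and include caregivers who stopped coaching without withdrawing consent. Place it late enough to cover the 16-week call period plus the expected lag to the first call. The documents do not state that lag; as an illustration only, an assumed lag of 1 to 4 weeks gives 16 + 1 = 17 to 16 + 4 = 20 weeks from randomisation. Record the actual assessment date and the patient's transplant status on that date.

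**Cost:** two or three sentences, a date trigger in REDCap and two recorded fields.

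**Downside:** caregivers who miss no calls are assessed about 4 to 5 weeks or more after their last call (16 − 12 or 16 − 11, and longer where their own lag is shorter than the one allowed for). The measure is then no longer strictly end-of-coaching. Some caregivers who run past 16 weeks may be assessed before their last call.

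### The secondary outcomes are planned only as description and change, with no coaching-minus-usual-care estimate, interval, baseline-adjusted model or stratum term

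*Combined protocol and SAP*

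**What the plan says.** The Data Analysis section declines a power statement because this is a pilot, then gives the whole analysis plan as "Data Analysis Plan: Descriptive statistics and change in secondary endpoints". The Endpoints section adds, for the secondary outcomes, "We will look at change in reported outcomes of stress, caregiver burden, resilience, quality of life, affect, and mastery", and states their purpose: "Preliminary efficacy data for power calculation for larger R01 application and multisite study".

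The design offers more than the plan uses. Under Study Design and Methods, caregivers are randomised to wellness coaching or to usual care, with randomisation stratified by the type of transplant awaited. Baseline questionnaires belong to the entry procedures, and after the intervention "all participants will be asked to complete the questionnaires a second time". Caregivers whose patient is transplanted during the coaching period stay in the study.

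The primary endpoint is a different matter: "Primary: Acceptability and feasibility of wellness coaching for caregivers of thoracic transplant candidates". Description is adequate for that, and this point does not touch it.

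**The concern.** A randomised, baseline-adjusted comparison is available from data the trial already collects, but the plan does not commit to one. The word change can be read in two ways.

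- **Difference between arms in mean change.** This is unbiased under randomisation. It uses the baseline by plain subtraction, which is less efficient than regression adjustment.
- **Change within the coaching arm.** This leaves the comparator unused. It mixes the coaching effect with anything else that moves scores over the period, such as time on the list or transplantation during follow-up.

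The stated aim, under Research Question and Aims, is to see whether coached caregivers improve. It mentions no comparison with usual care, so the second reading cannot be excluded. The choice matters because a two-arm power calculation needs a between-arm difference and its SD. If the quantity is left open until results are seen, the more favourable one can be picked.

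**Working it through.** The documents give no effect size, SD, alpha, allocation ratio or dropout, so there is no planned figure to reproduce. The only numerical input from them is the target of 60 caregivers (Subject Information).

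**Assumptions, none in the documents:** 1:1 allocation (n = 30 per arm), independent caregivers, equal SDs at both times (set to 1), and baseline/follow-up correlation ρ from 0.3 to 0.8.

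**Step 1. Precision under the between-arm reading.**

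- Change score: SE = √(2/n) × √(2(1 − ρ)), t on 2n − 2 = 58 df.
- ANCOVA: SE = √(2/n) × √(1 − ρ²), t on 2n − 3 − (L − 1) df, where L is the number of strata. This gives 56 df for two strata and 55 for three.

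Example at ρ = 0.5, with √(2/30) = 0.258: the change-score SE is 0.258 × √1.0 = 0.258, and the ANCOVA SE is 0.258 × √0.75 = 0.224. Multiplying by the t quantiles gives half-widths of 0.52 and 0.45.

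| ρ | SE, change | SE, ANCOVA | 95% half-width, change | 95% half-width, ANCOVA | Gain (SD) |
|---|---|---|---|---|---|
| 0.3 | 0.306 | 0.246 | 0.61 | 0.49 | 0.12 |
| 0.5 | 0.258 | 0.224 | 0.52 | 0.45 | 0.07 |
| 0.7 | 0.200 | 0.184 | 0.40 | 0.37 | 0.03 |
| 0.8 | 0.163 | 0.155 | 0.33 | 0.31 | 0.02 |

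The ANCOVA half-widths agree to two decimals for two or three strata. With an assumed 20% loss (24 per arm, two strata) the pairs are 0.69 and 0.56, 0.58 and 0.50, 0.45 and 0.42, and 0.37 and 0.35.

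The formulas treat the regression slope as known. A simulation of 6,000 trials per setting, with slope and strata estimated, gave mean half-widths at ρ = 0.5 and 30 per arm of 0.515 (change) and 0.450 (ANCOVA) with two equal strata. Coverage was 94% to 96% for both methods in all settings. No stratum effect was simulated, so this shows that the stratum term costs little, not what it gains.

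**Step 2. Consequence under the within-arm reading (illustration only).** Suppose the true difference is 0.4 SD and usual care improves by 0.1 or 0.2 SD. The coaching arm then shows a change of 0.5 or 0.6 SD. Sizing a later trial by n per arm = 2(1.960 + 0.842)²/d², for two-sided 5% and 80% power, gives:

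| d used for planning | n per arm | Power at true d = 0.4 |
|---|---|---|
| 0.4 | 99 | 80% |
| 0.5 | 63 | 61% |
| 0.6 | 44 | 47% |

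If usual care worsened, the error would run the other way.

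**The case against.** A pilot with a feasibility endpoint needs no confirmatory analysis, and the more natural reading of a randomised design that re-measures everyone is a between-arm comparison. On that reading the change score is unbiased, and with an interval it would serve a pilot. The advantage of ANCOVA shrinks to 0.02 SD at ρ = 0.8, and no benefit of the stratum term can be computed, because the documents give no stratum sizes or effects. All of this stands. It makes the covariates a refinement and the missing between-arm estimate with its interval the core of the point.

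The planning illustration is also open to challenge. It needs an assumed effect, an assumed usual-care shift, and planners who ignore their own comparator. It omits the sampling error of the recommended estimate. At ρ = 0.5 a result one SE (0.224) either side of 0.4 gives d = 0.624 or 0.176, hence 41 or more than 500 per arm. With a usual-care shift of only 0.1 SD, within-arm change even has a smaller root-mean-square error: √(0.183² + 0.1²) = 0.208 against 0.224. At a 0.2 SD shift it is larger, 0.271. So naming the right contrast does not secure a correct sample size for the next trial.

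None of this removes the omission. The protocol template itself asks for an endpoint analysis plan even when the work is exploratory, and the pilot justification given covers power only. Within-arm change remains the wrong quantity for a two-arm power calculation, whatever its variance.

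**Conclusion.** The concern holds. No section names a coaching-minus-usual-care estimate, an interval, a baseline-adjusted model or a stratum term for the secondary outcomes, although the design supports all of them and the results have a declared use that needs the first two.

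Under the between-arm reading the cost is precision only: 0.12 SD of half-width at ρ = 0.3, falling to 0.02 SD at ρ = 0.8. Under the within-arm reading the reported figure is off by the usual-care arm's own mean change, whose size and direction the documents cannot tell us. The sizes rest on the assumptions listed above, including one independent caregiver per patient. The protocol lets a patient nominate up to three, though equal accrual of patients and caregivers suggests one each. No data are lost either way. This is a worthwhile, low-cost improvement to an exploratory analysis.

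**What to change.** Keep description for the feasibility and acceptability endpoint. For each secondary scale collected, add to the Data Analysis section:

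- ANCOVA of the follow-up score on randomised arm, baseline score and the transplant-type strata used in randomisation. State the stratum levels, including where heart/lung candidates fall.
- Every caregiver with a follow-up score is analysed in the assigned arm, whatever number of calls was completed. The number without a follow-up score is reported by arm.
- The result is the adjusted coaching-minus-usual-care difference with 95% CI, labelled as estimation only. Within-arm change is given as description.
- The SD, baseline/follow-up correlation, retention and CI go forward to planning of the larger trial, so that the uncertainty travels with the estimate.

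The Study Measures list labels no instrument as measuring mastery, so one must be named before that outcome can be analysed.

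The cost is a few lines of wording, with no new data, contacts or caregivers. Residual degrees of freedom fall from 58 to 56 with two strata or 55 with three. The gain is small if the correlation is high, and the adjusted difference may look less favourable than the within-arm change.
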